**17.3 Describe any procedures that will be used for quality control of collected data.**

**Response: Double entry of data collected, for example clinical measurements and demographic information, will also be completed and compared for accuracy, and discrepancies will be resolved prior to data analysis.**

**Samples will be selected and testing results reported by laboratory number only. Laboratory number can be linked to ID number from limited-access study files with the linkage data stored on password protected computers.**

**Procedures are in place for quality control of the 16S sequencing and for data analysis.**

## 18.0        Confidentiality

### A. Confidentiality of Study Data

*Describe the local procedures for maintenance of confidentiality of study data and any records that will be reviewed for data collection.*

*18.1 A. Where and how will all data and records be stored? Include information about: password protection, encryption, physical controls, authorization of access, and separation of identifiers and data, as applicable. Include physical (e.g. paper) and electronic files.*

Response:

Paper records are kept in locked cabinets and/or in locked rooms in 120 and B20 Foster Hall. Computerized data sets are stored in study computers accessible only to authorized study personnel and are password protected.

Identity is coded and is not/will not be associated with any published results. Code number and identity will be kept in secured files of the Principal Investigator (see above). The only way participant identity would be revealed is through an on-site review, by an IRB representative, of clinical records to assess the accuracy and consistency with study/research records. S/he might see a name with other information, but they would not be allowed to take any clinical record with a name on it out of the secured area unless mandated by a judicial court. HIPAA policies and practices will be followed in the handling of patients' dental records and study documents.

Identifying data are kept in files separate from study data files for as long as there is any interest in re-contacting participants, such as for a follow-up study of some kind.

If data files will be used by others outside of the IRB-approved study group, the data files will be modified to include only identifiers permitted in the "de-identified" classification: gender, ethnicity, age (up to 89 years), year of birth and the first three digits of the zip code as long as the certification of de-identification criteria are met. Additional address information, telephone numbers, email addresses, social security numbers will not be included. We do not collect insurance data, vehicle identifiers, device identifiers, URLs, IP address numbers, voice or finger prints, or photos of participants so they will not be included in the saved data files.

All study staff are trained in all study procedures and must receive all training required of the Institutional Review Board at UB and School of Dental Medicine. All data files are stored on password-protected computers and access to those computers is limited to authorized study staff only.

Study/research files will be kept by identification (ID) number only. Laboratory numbers are different than ID numbers and the linkage will be stored in limited access files on password-protected computers.

**Informed Consents are kept separate from study/research charts in limited access (locked) rooms.**

18.2 *A. How long will the data be stored?*

Response: **Until analyzed or indefinitely.**

18.3 *A. Who will have access to the data?*

Response: **Authorized study staff.**

18.4 *A. Who is responsible for receipt or transmission of the data?*

Response: **The PI or authorized PI representative.**

18.5 *A. How will the data be transported?*

Response: **Data will be transported on CDs or flash drives in password protected files. If needed, the CDs can be sent via USPS, FedEx or UPS for data transfer to a more distant person.**

## **B. Confidentiality of Study Specimens**

*Describe the local procedures for maintenance of confidentiality of study specimens.*

**N/A:** No specimens will be collected or analyzed in this research.  
(*Skip to Section 19.0*)

18.6 *B. Where and how will all specimens be stored? Include information about: physical controls, authorization of access, and labeling of specimens, as applicable.*

Response: **Samples are labeled with participant study number, sample number, type of sample, study visit, date and study. Only authorized study personnel handle samples.**

**Samples will be stored, by study, in -80° C freezers in B20 Foster Hall until tested. These rooms are locked, and access is limited to authorized study staff. All freezers are monitored daily for temperature and are on a University alarm system in case they fail.**

18.7 *B. How long will the specimens be stored?*

Response: **Until tested or indefinitely.**

18.8 *B. Who will have access to the specimens?*

Response:

**Authorized study personnel.**

18.9 *B. Who is responsible for receipt or transmission of the specimens?*

Response:

**Authorized study personnel.**

18.10 *B. How will the specimens be transported?*

Response:

Samples and data will be labeled and identified only by ID number. Samples will be transported frozen on dry ice unless the frozen state is not needed. Data will be housed on limited-access password-protected computers backed up by UB systems. If needed, data will be copied onto CDs and sent via USPS, FedEx or UPS.

## **19.0 Provisions to Monitor the Data to Ensure the Safety of Subjects**

- N/A:** This study is not enrolling subjects, or is limited to records review procedures only. This section does not apply.

**NOTE: Minimal risk studies may be required to monitor subject safety if the research procedures include procedures that present unique risks to subjects that require monitoring. Some examples include: exercising to exertion, or instruments that elicit suicidality or substance abuse behavior. In such cases, N/A is not an acceptable response.**

19.1 *Describe the plan to periodically evaluate the data collected regarding both harms and benefits to determine whether subjects remain safe.*

Response:

Data collected during the study will be reviewed by the PI and investigators (primarily for clinical issues). These reviews will take place after six months of participant recruitment and every six months thereafter.

19.2 *Describe what data are reviewed, including safety data, untoward events, and efficacy data.*

Response: Study accrual, reports of adverse and serious adverse events and unanticipated problems will be reviewed by the investigators.

19.3 *Describe any safety endpoints.*

Response:

**Adverse and serious adverse events, untoward events will be assessed by asking about changes in status and new events since last visit.**

*19.4 Describe how the safety information will be collected (e.g., with case report forms, at study visits, by telephone calls with participants).*

**Response:** When subjects return for study visits, they will be queried about changes in their medical and dental status, untoward events, new medications etc. This information will be recorded on study visit checklists and progress notes and used when data are reviewed by the PI, investigators and study staff.

*19.5 Describe the frequency of safety data collection.*

**Response:** Data will be collected at the study visits and will start at the beginning of the study.

*19.6 Describe who will review the safety data.*

**Response:** The PIs and Investigators, coordinator.

*19.7 Describe the frequency or periodicity of review of cumulative safety data.*

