**Response:**

**After six months and every six months thereafter.**

*19.8 Describe the statistical tests for analyzing the safety data to determine whether harm is occurring.*

**Response:** All adverse events (serious and non-serious) reported during a study will be taken into account when analyzing study data, and will be included in the final study report. Identification of serious adverse effects (SAEs) will be used to identify, during the conduct of the study, those adverse events that may require an expedited reporting procedure to regulatory authorities. No testing of drugs will be used. Therefore, statistical tests will be used to evaluate SAEs only if events are serious.

*19.9 Describe any conditions that trigger an immediate suspension of the research.*

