**Response:** **Inform the participant verbally and document in chart progress notes.**

20.3 *Describe procedures that will be followed when subjects withdraw from the research, including retention of already collected data, and partial withdrawal from procedures with continued data collection, as applicable.*

**Response:** **Participants will be asked if they wish to withdraw from all components of the study or if they will allow follow-up activities. For observational studies such as this one, withdrawal is not likely, but participants who want to withdraw will be asked if any samples already collected may be used in the research. If participant does NOT want those samples used, those samples will be destroyed.**

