**Dental radiographs:** About 18 radiographs will be taken. These x-rays will not be taken if suitable x-rays taken in the past two years are available to review, or if the dental clinician feels there is no clinical need for them. The amount of radiation exposure from the dental x-rays in this study is about 17.1 millirem (or 0.017 rem). This amount is below the 5 rem per year allowed for research participants by the National Institutes of Health (NIH) Radiation Safety Committee. The average person in the United States has a radiation exposure of about 0.36 rem per year from natural sources, such as the sun, outer space, and earth's air and soil. When taking x-rays, the lowest dose possible will be used and participants will wear a lead apron to reduce exposure.

Although there is no direct evidence that the amount of radiation exposure from participating in this study is harmful, there is indirect evidence that it may not be completely safe. There may be a very slightly increased risk of cancer.

Paroex® is a non-alcohol chlorhexidine preparation. With use of chlorhexidine, there is risk of reversible staining of teeth and the possibility of some alteration in taste. There is increased likelihood of staining in smokers, coffee drinkers and those who are susceptible to teeth staining in general. The cleaning of the front teeth that will be

**provided at the 3-month visit will help to reduce any staining that may occur. If there is any alteration in taste, it should go away when use of chlorhexidine stops. Paroex® was approved by the FDA November 29, 2005 (application # (ANDA) 076434).**

**Soft-Picks may cause some bleeding of the gums at first usage, but the bleeding should lessen and stop as use is continued (as gums heal). Soft-Picks are a readily available consumer product sold in supermarkets and drug stores. They are “510(k) exempt” from requiring FDA approval.**

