**Response: An operatory in the PDRC.**

*26.3 Describe how you will ensure that subjects are provided with a sufficient period of time to consider taking part in the research study.*

*NOTE: It is always a requirement that a prospective subject is given sufficient time to have their questions answered and consider their participation. See "SOP: Informed Consent Process for Research (HRP-090)" Sections 5.5 and 5.6.*

**Response: Subjects will be given the opportunity to ask as many questions as they need to be comfortable prior to signing the consent form. Subjects will be asked to provide or decline consent within 24 hours of having the study explained in detail.**

*26.4 Describe any process to ensure ongoing consent, defined as a subject's willingness to continue participation for the duration of the research study.*

**Response: If a participant presents for a study visit we assume they are consenting to continue in the study; however, we will add a question to our study visit checklists asking, "Participation in this study is voluntary. Do you continue to consent to being in this study?" to make sure there is not confusion regarding continuing consent to participate in a research study. If it is the first visit, the first thing we do is obtain consent. As we proceed through the first, and all visits, we ask the question above. At the end of the first visit, we make the appointment for the second visit and we also make a reminder phone call the day or two before the second visit. We usually speak to the participants during the call so they again have the opportunity to say they do not want to continue or they need a new appointment date and/or time.**

**If a participant does not show up for a visit and cannot be reached and continues this behavior, we try to reach them by phone and email and, if no response, eventually by registered mail with a postage-paid envelope so they can send us an answer about continuation. In the past, some participants have had personal or family problems arise and some have continued with adjustment of visit timing; others have chosen to withdraw or we withdrew them.**

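### Harms are asked about at visits three months apart, and no harm question is written into the exit steps or no-show contacts, so harms behind drop-out may go uncounted

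*Combined protocol and SAP*

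**What the plan says.** Three answers in section 19.0 set the rule for harms. Section 19.3: "Adverse and serious adverse events, untoward events will be assessed by asking about changes in status and new events since last visit". Section 19.4: "When subjects return for study visits, they will be queried about changes in their medical and dental status, untoward events, new medications etc", and on where the answers go, "This information will be recorded on study visit checklists and progress notes". Section 19.5: "Data will be collected at the study visits and will start at the beginning of the study".

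The visit lists in 10.1 place the adverse event questionnaire at months 3, 6, 9 and 12. Scaling and root planing (SRP) follows within a month of Baseline, with no harm question listed for it.

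For people who leave, 20.1 covers withdrawal decided by the study, and 20.2 gives the exit step: "Inform the participant verbally and document in chart progress notes". Section 20.3 covers people who choose to withdraw. They are asked how far they wish to withdraw and whether samples already taken may be used. For people who do not attend, 26.4 describes phone and email attempts, then a letter sent "eventually by registered mail with a postage-paid envelope so they can send us an answer about continuation".

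Section 19.8 expects serious events to be identified while the study runs, so as to pick out "those adverse events that may require an expedited reporting procedure to regulatory authorities". Section 21.1 names the product harms: "With use of chlorhexidine, there is risk of reversible staining of teeth and the possibility of some alteration in taste", and some gum bleeding when Soft-Picks are first used.

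**The concern.** A participant who stops because of a harm is the person least likely to attend the next visit, and the visit is where the plan asks. If nothing is asked at exit or when a no-show is contacted, the missing harm data are informative: they are missing because of the harm.

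The loss need not be even across the treatment comparison. SRP is given to all four groups, so missing its harms lowers the recorded rate on both sides. Chlorhexidine staining, taste change and early bleeding from Soft-Picks concern products given only to Groups A and B. Losing those tends to make supportive periodontal therapy (SPT) look better tolerated than it is.

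The first interval is the most exposed. It contains SRP and first use of both products, and the first scheduled questionnaire comes at its end. Timing matters too: a serious event soon after a visit may not be asked about until the next one.

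**Working it through.** The plan gives no harm rate and no reasons for leaving, so there is no figure of its own to reproduce. The check traces each contact and then shows a range under stated assumptions.

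**1. Contacts and whether a harm question is written for them**

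| Contact | Section | Harm question stated? |
|---|---|---|
| SRP, within a month of Baseline | 10.1 | No |
| Months 3, 6, 9, 12 | 10.1 | Yes (taste part not listed at 12) |
| Reminder call, a day or two before a visit | 26.4 | No |
| Phone, email, registered mail to no-shows | 26.4 | No; concerns continuation |
| Withdrawal decided by the study | 20.1, 20.2 | No; notice and chart note |
| Withdrawal chosen by the participant | 20.3 | No; extent of withdrawal and use of samples |

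**2. Delay.** Visits at 0, 3, 6, 9 and 12 months leave gaps of 3 months. An event just after a visit is first asked about up to 3 months later (mean 1.5 if event times are uniform), up to 6 after one missed visit and up to 9 after two. If the person does not return, no scheduled question follows.

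**3. Leavers.** Groups A and B: 2 × 26 = 52 (5.1, 17.2). Attrition is 10% (17.2): 0.10 × 52 = 5.2.

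**4. Participants missed.** Let s be the assumed share of these leavers who left because of a harm that nobody recorded. Missed = 5.2 × s. As a fraction of all affected participants, it is missed / (missed + recorded), shown here for an assumed 5 participants with a recorded harm.

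| s | Missed | Percentage points of 52 | Fraction of affected missed |
|---|---|---|---|
| 25% | 1.3 | 2.5 | 1.3/6.3 = 21% |
| 50% | 2.6 | 5.0 | 2.6/7.6 = 34% |
| 100% | 5.2 | 10.0 | 5.2/10.2 = 51% |

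**5. Effect on the recorded rate.** Take an assumed true count of 10 of 52 (19.2%). Recorded rate = (10 − lost)/(52 − lost).

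- If leaving is spread evenly over 12 months, 5.2 × 3/12 = 1.3 leave before month 3. One affected early leaver lost: 9/51 = 17.6%.
- Two lost: 8/50 = 16.0%.
- All five leavers affected and unrecorded: 5/47 = 10.6%.

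**6. Base.** Section 5.1 describes the 104 as having complete data, while 17.2 speaks of enrolling a minimum of 104. If 52 means completers, enrolment is 52/0.9 = 57.8 and leavers number 5.8. The percentage points in step 4 do not change.

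**The case against.** The strongest reply is that a harm behind drop-out is not bound to be lost. Section 19.8 takes into account all adverse events reported during the study, without limiting this to those reported at visits. Progress notes feed the safety review (19.4), and exits are written in progress notes (20.2). Withdrawal in the participant's clinical interest (20.1) means staff may already know of a harm, and 20.3 lets people who withdraw agree to further follow-up. A reader might infer that these harms are never counted; the documents do not support that. They show that such harms are not systematically asked about.

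A reader might also infer that 19.8 is contradicted, or that serious events have no route to the centre between visits. Section 19.8 sets no reporting deadline that quarterly questioning would breach. The consent pages are not in the reviewed text, and the Manual of Procedures is a separate upload; either may tell participants to call. All that can be said is that the protocol text gives no such route.

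The scale can fairly be disputed. Missing half the affected participants requires every SPT leaver to have had an unrecorded harm. People who leave after month 3 will usually have answered the questionnaire at least once. Harms are not a primary or secondary endpoint, the study is described as a pilot, and the rinse is approved and used as labelled.

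These points limit the wording and the size. They do not supply a harm question at exit or in the no-show contacts. The remark in 20.3 that withdrawal is unlikely in an observational study like this one does not help either, because 4.1 describes a randomised trial and 17.2 allows for 10% attrition.

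**Conclusion.** The point holds in a limited form. The written rule collects harms by asking at visits, and no question on harm or the reason for stopping is stated for either exit route or for the no-show contacts. Harms that lead to drop-out may therefore go uncounted, and any loss of product harms would tend to bias the recorded SPT rate downward.

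The size cannot be known from the documents. The range of about 1 to 5 participants rests on the plan's 10% attrition applying to Groups A and B, an assumed 25% to 100% of leavers leaving because of a harm, and none of those harms being recorded. The lower part of the range is the more plausible if leaving is spread over the year.

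On timing, the first scheduled question may come up to 3 months after an event. Whether serious events would in practice reach the centre sooner depends on documents outside the reviewed text. Sample size, power and alpha are unaffected. This is a cheap improvement worth making, not a flaw that undermines the trial.

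**What to change.** - In 19.4, 19.5, 20.2, 20.3 and 26.4, state that the questions on the existing AE, Taste and Compliance form (10.4), plus the reason for stopping, are asked at withdrawal of either kind and at each no-show contact already made: phone call, email and the registered-mail reply.
- Ask the same harm questions at the SRP appointment, which falls in the first interval.
- In 19.4, state that participants report serious events to the centre when they occur and that the date the centre became aware is recorded. If the consent form or the Manual of Procedures already says this, a cross-reference is enough.

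The reminder call need not carry the questions, since it comes only a day or two before a visit.

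The cost is wording in five sections, a reply sheet in a letter that already has a return envelope, and a few minutes of staff time per contact, which matters a little in a study that is now unfunded. Answers by phone or mail will be less detailed than those given in clinic. No visit is added.

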**Response:**

**After six months and every six months thereafter.**

*19.8 Describe the statistical tests for analyzing the safety data to determine whether harm is occurring.*

**Response:** All adverse events (serious and non-serious) reported during a study will be taken into account when analyzing study data, and will be included in the final study report. Identification of serious adverse effects (SAEs) will be used to identify, during the conduct of the study, those adverse events that may require an expedited reporting procedure to regulatory authorities. No testing of drugs will be used. Therefore, statistical tests will be used to evaluate SAEs only if events are serious.

*19.9 Describe any conditions that trigger an immediate suspension of the research.*

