**BASELINE VISIT:**

- 1. Review medical and dental histories.**
- 2. Baseline Taste Test**
- 3. Oral Health Examination:**
  - a) Plaque Index (PI)**
  - b) Probing Pocket Depth (PPD)**
  - c) Bleeding on Probing (BOP)**
  - d) Gingival Index (GI)**
  - e) Clinical Attachment Level (CAL)**
- 4. Collect samples:**
  - a) Blood (FBS, HbA1c, Insulin, hs-CRP and microbiome testing, and for future testing of C-peptide, proinsulin, total GLP-1, PYY,**

DPP-IV, glucagon, LPS, soluble-TNF $\alpha$  RI and RII, MGO, TMAO, creatinine, and for future unknown testing.

- b) Subgingival plaque and saliva.
- c) Fecal, skin, and vaginal samples

3. Treatment: All participants will receive full mouth SRP within one month of the baseline visit.

4. Oral health instruction: All participants will receive oral hygiene instruction from the hygienist.

5. Participants will be randomized into one of the four groups.

6. Groups A and B will receive the product, Soft-Picks, and information on how to use them.

7. Make an appointment for 3 months after Baseline Visit.

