**12-MONTH VISIT:**

**1.** Collect the unused Soft-Picks from the subjects in Groups A and B.

**2.** Review medical and dental histories.

**3.** Ask the subjects to answer the Adverse Event, and Compliance questionnaire.

**4.** Weight

**5.** Taste Test.

**6.** Oral health examination

7. **Collect samples: blood (FBS, HbA1c, Insulin, hs-CRP and microbiome testing, and for future testing of C-peptide, proinsulin, total GLP-1, PYY, DPP-IV, glucagon, LPS, soluble-TNF $\alpha$  RI and RII, MGO, TMAO, creatinine, and for future unknown testing), subgingival plaque, saliva, fecal, skin, and vaginal samples.**

8. **Finish Study: Participants will receive a dental cleaning (prophy) and be referred to a dentist for any necessary dental treatment needed.**

*10.2 Describe what data will be collected.*

*NOTE: For studies with multiple data collection points or long-term follow up, consider the addition of a schedule or table in your response.*

Response:

1. **Demographic information: age, date of birth, gender, racial and ethnic background**
2. **Medical History with Concomitant Medications**
3. **Dental History with Questionnaire to Assess Likelihood of Periodontal Disease**
4. **Height and Weight**
5. **Results of oral health examination and periodontal disease measurements**
6. **History of cigarette smoking and alcohol intake**
7. **Results of blood testing**
8. **Results of microbiome testing**

 *10.3 List any instruments or measurement tools used to collect data (e.g. questionnaire, interview guide, validated instrument, data collection form).*

*Include copies of these documents with your submission.*

Response:

1. **Medical History with Concomitant Medications**
2. **Dental History with Questionnaire to Assess Likelihood of Periodontal Disease**
3. **Forms – uploaded to Click as file “DM RCT Manual of Procedures”**
  - a. **Height and Weight Form**
  - b. **Blood Collection Form**
  - c. **Saliva Collection Form**

- d. **Clinical Report Form for Charting Teeth Status and Periodontal Measurement Results**
- e. **Plaque Collection Form**
- f. **Fecal Collection Information Form**
- g. **Vaginal Swab Collection Form**
- h. **Taste Test Scoring Form**

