## **31.0      Drugs or Devices**

- N/A:** This study does not involve drugs or devices. This section does not apply.

*31.1 If the research involves drugs or devices, list and describe all drugs and devices used in the research, the purpose of their use, and their regulatory approval status.*

Response: Paroex® mouthrinse, FDA approved and used according to labeling. Soft-Picks, 510(k) exempt and available over the counter.

Here are the links: Paroex®: <http://us-professional.gumbrand.com/gumr-chlorhexidine-gluconate-oral-rinse-4.html>

Soft-Picks: <http://www.sunstar.com/rd/story/soft-picks-advanced>; <http://www.gumbrand.com/gum-soft-picks-40-ct-632rc.html>; and <http://www.soft-picks.com/about-soft-picks>.

<http://us-professional.gumbrand.com/gumr-chlorhexidine-gluconate-oral-rinse-4.html>

Sunstar, Inc. has ownership of these products.

*31.2 Describe your plans to store, handle, and administer those drugs or devices so that they will be used only on subjects and be used only by authorized investigators.*

Response: Paroex® and Soft-Picks will be stored in our limited access, locked cool room adjacent to the PDRC.

*If the drug is investigational (has an IND) or the device has an IDE or a claim of abbreviated IDE (non-significant risk device), include the following information:*

*31.3 Identify the holder of the IND/IDE/Abbreviated IDE.*

Response: The Paroex® mouthrinse and Soft-Picks to be used in this study are not investigational. Paroex® mouthrinse is FDA approved and will be used according to labeling. Soft-Picks are like small tooth brushes and are readily available over the counter.

*31.4 Explain procedures followed to comply with FDA sponsor requirements for the following:*

	Applicable to:		
FDA Regulation	IND Studies	IDE studies	Abbreviated IDE studies
21 CFR 11	X	X	
21 CFR 54	X	X	
21 CFR 210	X		
21 CFR 211	X		
21 CFR 312	X		
21 CFR 812		X	X
21 CFR 820		X	

Response: N/A

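### Section 19.8 confines statistical evaluation of safety to serious events because no drug is tested, and no between-arm comparison of the rinse's expected non-serious harms is specified

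*Combined protocol and SAP*

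**What the plan says.** Section 19.8, on statistical tests for safety data, makes two statements. The first is inclusive: "All adverse events (serious and non-serious) reported during a study will be taken into account when analyzing study data", and these events are to appear in the final report. The second sets the testing rule and its reason: "No testing of drugs will be used. Therefore, statistical tests will be used to evaluate SAEs only if events are serious".

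Other sections bear on that reason and that rule:

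- **Intervention.** Section 1.1 makes the efficacy of SPT (the 0.12% chlorhexidine rinse with Soft-Picks) after SRP the main goal. Section 4.1 gives SPT to Groups A and B. Section 31.1 lists the rinse under drugs or devices: "Paroex® mouthrinse, FDA approved and used according to labeling". Section 31.3 adds that neither product is investigational.
- **Expected harms.** Section 21.1 states: "With use of chlorhexidine, there is risk of reversible staining of teeth and the possibility of some alteration in taste". For Soft-Picks it expects some gum bleeding at first use.
- **Safety endpoints.** Section 19.3 is generic: "Adverse and serious adverse events, untoward events will be assessed by asking about changes in status and new events since last visit".
- **Taste data.** Section 10.1 lists a Taste Test at Baseline and at 3, 6, 9 and 12 months. Sections 10.3 and 10.4 list a scoring form for it.
- **Endpoints and analysis.** Section 2.1 names no taste or staining endpoint. Section 17.1 describes the pilot's statistics as descriptive, and the comparisons it names concern oral bacteria.

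**The concern.** The restriction rests on a premise that does not match the design. A drug product is part of what is being evaluated, and it is given by group. The harms the protocol itself attributes to that product fall in the class of events the rule leaves without a statistical evaluation. The class it keeps, serious events, is not one that Section 21.1 leads a reader to expect from a rinse and interdental picks.

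At stake is the balance of the report. It could describe a pocket-depth benefit of adding SPT with no prespecified comparison of SPT's known drawbacks, although a taste measure with a baseline value is collected in all groups. The study is meant to inform a larger trial, and tolerability by arm belongs in that preliminary information.

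**Working it through.** The plan gives no figure on this point to reproduce. The check is a comparison of sections, followed by arithmetic on how much a by-arm estimate could show.

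**1. Does the premise hold?** Section 19.8 says no drugs are tested. Sections 1.1 and 4.1 evaluate a regimen containing the rinse, and Section 31.1 lists the rinse as an approved product. If the sentence means that no investigational drug is tested, it agrees with Section 31.3. The inference still fails: approval status does not decide whether the intervention's known side effects should be compared between arms.

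**2. Is the gap filled elsewhere?** Sections 2.1, 17.1 and 19.3 specify no comparison of taste, staining or gum bleeding between SPT and SRP alone.

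**3. How much taste information is collected?** Five occasions × 104 participants = 520 planned assessments. Section 10.1 lists collection of the rinse bottle only at month 3; at 6, 9 and 12 months it lists only Soft-Picks. The documents do not state how long the rinse is used. If exposure ended at month 3, the assessments bearing most directly on the rinse would be Baseline and month 3: 2 × 104 = 208.

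**4. What could a by-arm difference in proportions show?** Inputs: 26 per group (Section 17.2), so 2 × 26 = 52 per arm if all contribute data. Event rates of 20% and 5% are assumed for illustration, since the documents give none.

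- Unpooled SE = √(0.20×0.80/52 + 0.05×0.95/52) = √(0.2075/52) = 0.0632
- 95% CI = 0.15 ± 1.96 × 0.0632 = 0.03 to 0.27
- Pooled rate = 0.125; null SE = √(2×0.125×0.875/52) = 0.0649
- Power (two-sided 0.05) = Φ[(0.15 − 1.96×0.0649)/0.0632] = Φ(0.36) ≈ 64%

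With 52 per arm and 80% power, the detectable SPT rate is about 19%, 24% or 32% for an assumed SRP-alone rate of 2%, 5% or 10%.

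Among diabetics only (A versus C, 26 per arm), the 20% versus 5% example gives SE = √(0.2075/26) = 0.0893, a 95% CI of about −3 to 33 points, and power of about 37%.

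**5. And a difference in Taste Test score?** If the score is treated as continuous, the standardised difference detectable with 80% power at 52 per arm is √(2/52) × (1.96 + 0.84) ≈ 0.55.

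**6. What does the retained category offer?** The chance of at least one participant with a serious event among 104 is 1 − (1 − r)^104: 41%, 65% or 88% for assumed risks r of 0.5%, 1% or 2%. At 1% the expected number is 104 × 0.01 ≈ 1, too few for a useful comparison.

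**The case against.** The strongest defence has three parts.

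- **Wording.** Section 31.3 suggests that Section 19.8 meant no investigational drug. That may well be so, and it makes the sentence a slip of wording. It does not support the restriction drawn from it.
- **Pilot status.** Section 17.1 limits the statistics to description, and even the primary pocket-depth endpoint has no named test. This stands against demanding hypothesis tests. It does not stand against by-arm estimates with intervals, which are descriptive.
- **Reporting promise.** Section 19.8 says non-serious events will be taken into account and reported. This stands, but it names no contrast, measure or method.

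Several stronger readings are tempting, and the documents do not support them:

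- A reader might infer that taste and staining will never be compared. The documents show only that no comparison is specified.
- A reader might infer that Section 19.8 bars analysis of Taste Test scores. It concerns adverse events and does not mention the Taste Test, whose purpose the documents do not state. Its relevance to harm is inferred from Section 21.1.
- A reader might infer that taste questions are dropped at month 12, where the text reads "Ask the subjects to answer the Adverse Event, and Compliance questionnaire". Section 10.4 lists one combined adverse event, taste and compliance form, so this may be an editing slip, and the Taste Test is still done at that visit.
- A reader might infer that the month-3 anterior cleaning removes stain unrecorded. The adverse event questionnaire and oral examination precede the cleaning in that visit's list, so stain could be captured as an adverse event, although no stain measure is named.

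**Conclusion.** The point holds in a limited form. Section 19.8 states a rule that restricts statistical evaluation to serious events, on a premise at odds with Sections 1.1, 4.1 and 31.1. No section specifies a between-arm comparison of the expected non-serious harms or of the Taste Test scores. The primary endpoint is unaffected.

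The gain from correcting this is moderate. A reader might infer from the illustrative interval of 3 to 27 points, which excludes zero, that the trial would reliably detect such a harm. Power of about 64% does not support that, and the diabetic-only comparison is weaker still. Nor is it established that all 520 taste assessments bear on the rinse. These figures rest on 52 per arm with complete data and on assumed event rates. The case for the change rests on the text and on estimates from data already planned, not on power.

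**What to change.** In Section 19.8, delete the statement that no drugs are tested and the restriction that follows from it. State instead that the following will be presented for SPT (A and B) versus SRP alone (C and D), as differences with 95% confidence intervals:

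- the proportion of participants with each expected non-serious event: taste alteration, staining reported as an adverse event, and gum bleeding;
- the change in Taste Test score from Baseline.

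Make month 3 the main time point, because rinse bottle collection is listed only there, and treat later visits as supportive. Label the results as descriptive estimates. In Section 2.1, list change in Taste Test score as a secondary safety outcome.

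Two additions are optional: a yes/no stain field completed before the month-3 cleaning, and aligning the 12-month questionnaire wording with the combined form in Section 10.4.

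The core change needs wording in two sections and no new data collection. Its cost is one extra table and one more secondary comparison to report.
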